8.6 Treatment Compliance

The Investigator is required to ensure compliance with respect to the KHK4083 (or placebo) dosing schedule required by the protocol. At least five of six IV infusions of investigational product are required to be administered during Induction Therapy for treatment compliance in this study. At least half of the IV infusions of investigational product are required to be administered during OLE/LTE Therapy for treatment compliance in this study.

8.6.1 Study Visit Outside of Planned Scheduled - Delay in Dosing

During Induction Therapy, investigational product (KHK4083 or placebo) will be administered every 2 weeks, for a total of 6 doses. A visit window, ± 2 days at Week 2, and ± 4 days for all other doses, has been defined. If the study visit/dosing does not occur during the planned visit window, investigational product should not be administered at the visit and

the next dose should be administered at the next visit. KHK4083 or placebo should not be administered less than 6 days from the previous dosing.

9 STUDY PROCEDURES

It is important to maintain the visit structure as accurately as possible. Whenever an adjustment to this structure is necessary, the date of the adjusted visit should occur within the number of days (before or after) specified in the planned schedules for Screening, Induction Therapy, and Induction Therapy Post-treatment Follow-up Period (refer to Study Schedule of Events, Table 9-1) and for OLE/LTE Therapy and OLE/LTE Therapy Post-treatment Follow-up Period (refer to Study Schedule of Events, Table 9-2). The timing of any subsequent visits should be scheduled to maintain the visit structure relative to the first day that investigational product was administered.

Screening evaluations used to determine the subject's study eligibility must be completed within the Screening Period (Day -28 to Day -1) prior to starting treatment on Day 1 (Week 0) unless otherwise specified. Written informed consent must be obtained prior to any study-specific procedures. Results of all Screening evaluations must be reviewed by the Investigator or his/her designee to ensure that all eligibility criteria have been satisfied prior to randomization. For subjects who complete double-blind Induction Therapy and are eligible at Week 12 to receive treatment, additional criteria are required for enrollment in OLE/LTE Therapy (refer to Section 7.4 for the list of criteria).

All efficacy, PK, PD, immunogenicity, and safety measurements obtained during the course of the study are summarized in Table 9-1, Table 9-2, Table 10.4.1-1, and Table 10.4.1-2.

Table 9-1 Study Schedule of Events - Screening, Induction Therapy, and Follow-up Period

Procedure	Screening Day -28 to Day -1	Treatment Period - Double-blind Induction Therapy: Weeks 0 to 12 (Last dose at Week 10) ^a (All Randomized Subjects)							Induction Therapy Post-treatment Follow-up Period for Subjects Not Enrolling in OLE Therapy		
		Baseline						End-of- Induction Therapy	Follow- up 1	Follow- up 2	Follow- up 3
		Week 0 Day 1	Week 2 ± 2 days	Week 4 ± 4 days	Week 6 ± 4 days	Week 8 ± 4 days	Week 10 ± 4 days	End-of- Treatment Week 12 ± 4 days	Week 16 ± 7 days	Week 20 ± 7 days	End-of- Study Week 26 ± 7 days
Written Informed Consent	X										
Inclusion/Exclusion Criteria	X	X									
Medical, Diet & Surgical History/ Demographics	X										
Physical Examination ^b	X	X						X			
Brief Physical Examination ^c			X	X	X	X	X		X	X	X
Vital Signs ^d	X	X	X	X	X	X	X	X	X	X	X
Body Weight	X	X	X	X	X	X	X	X	X	X	X
Height	X										
12-lead ECG	X	X ^e				X ^e	X ^e				
Hematology (CBC with diff & platelets)	X	X	X	X	X	X	X	X	X	X	X
Serum Chemistry Profile	X	X	X	X	X	X	X	X	X	X	X
Coagulation Profile	X	X						X			
Multiplex-31 Assay ^f		X	X					X			
Urinalysis	X	X	X	X	X	X	X	X	X	X	X
Serum FSH ^g	X										
Serum Pregnancy ^g	X										
Urine Pregnancy ^g		X		X		X		X	X	X	X
Urine Drug Screen	X										

Table 9-1 Study Schedule of Events - Screening, Induction Therapy, and Follow-up Period

Procedure	Screening Day -28 to Day -1	Treatment Period - Double-blind Induction Therapy: Weeks 0 to 12 (Last dose at Week 10) ^a (All Randomized Subjects)						Induction Therapy Post-treatment Follow-up Period for Subjects Not Enrolling in OLE Therapy			
		Baseline						End-of- Induction Therapy	Follow- up 1	Follow- up 2	Follow- up 3
		Week 0 Day 1	Week 2 ± 2 days	Week 4 ± 4 days	Week 6 ± 4 days	Week 8 ± 4 days	Week 10 ± 4 days	End-of- Treatment Week 12 ± 4 days	Week 16 ± 7 days	Week 20 ± 7 days	End-of- Study Week 26 ± 7 days
Stool Enteric Pathogens (including Clostridium difficile)	X							X			
Hemoglobin A1c	X										
HIV Test; Hepatitis B (core antibody or surface antigen); Hepatitis C antibody	X										
PPD (or QuantiFERON)- TB ^h	X										
Delayed-type Hypersensitivity Skin Test ⁱ (US and other selected countries)	X						X				
Randomization		X									
Diary Training	X										
Partial Mayo Clinic Score (without sigmoidoscopy, includes review of diary) with Physician's Global Assessment		X	X	X	X	X	X	X	X	X	X

Table 9-1 Study Schedule of Events - Screening, Induction Therapy, and Follow-up Period

Procedure	Screening Day -28 to Day -1	Treatment Period - Double-blind Induction Therapy: Weeks 0 to 12 (Last dose at Week 10) ^a (All Randomized Subjects)							Induction Therapy Post-treatment Follow-up Period for Subjects Not Enrolling in OLE Therapy		
		Baseline						End-of- Induction Therapy	Follow- up 1	Follow- up 2	Follow- up 3
		Week 0 Day 1	Week 2 ± 2 days	Week 4 ± 4 days	Week 6 ± 4 days	Week 8 ± 4 days	Week 10 ± 4 days	End-of- Treatment Week 12 ± 4 days	Week 16 ± 7 days	Week 20 ± 7 days	End-of- Study Week 26 ± 7 days
Flexible Sigmoidoscopy with biopsy for mMES, UCEIS, modified Baron score & total Mayo Clinic score (includes review of diary)	X (within 7 to 28 days prior to first dose)							X ^j (recommend 7 to 13 days prior to Week 12 LTE dosing)			
IBDQ		X	X	X	X	X	X	X	X	X	X
Fecal Calprotectin ^k		X	X					X			
wr-CRP Assay		X	X	X	X	X	X	X			X
Pharmacokinetics		For PK Sample Collection Schedule Refer to Table 10.4.1-1 for Cohorts 1 - 3 during Induction Therapy (Part A) and LTE and Table 10.4.1-2 for Cohort 4 during Induction Therapy (Part B) and LTE									
Anti-KHK4083 Antibodies ^l		X	X	X	X	X	X	X	X	X	X
Flow Cytometry		Refer to Table 10.4.1-1 for Cohorts 1 - 3 and Table 10.4.1-2 for Cohort 4									
Future Biomarker Analyses (whole blood) ^m		X	X					X			X
Adverse Events ⁿ	X	X	X	X	X	X	X	X	X	X	X
Prior/Concomitant Medications ^o	X	X	X	X	X	X	X	X	X	X	X
Investigational Product Administration ^a On-site (plus phone call) Post-infusion Monitoring Required^p		X	X	X	X	X	X				

Table 9-1 Study Schedule of Events - Screening, Induction Therapy, and Follow-up Period

Procedure	Screening	Treatment Period - Double-blind Induction Therapy: Weeks 0 to 12 (Last dose at Week 10) ^a (All Randomized Subjects)							Induction Therapy Post-treatment Follow-up Period for Subjects Not Enrolling in OLE Therapy		
		Baseline						End-of- Induction Therapy	Follow- up 1	Follow- up 2	Follow- up 3
	Day -28 to Day -1	Week 0 Day 1	Week 2 ± 2 days	Week 4 ± 4 days	Week 6 ± 4 days	Week 8 ± 4 days	Week 10 ± 4 days	End-of- Treatment Week 12 ± 4 days	Week 16 ± 7 days	Week 20 ± 7 days	End-of- Study Week 26 ± 7 days
Determine if Eligible for OLE at Week 12								X			

Footnotes to Table 9-1.

- a: Induction Therapy Dosing Regimen: Part A Cohorts 1 - 3 (KHK4083: 1.0, 3.0, and 10 mg/kg or placebo) once every 2 weeks (Weeks 0 to 10); and Part B Cohort 4 (KHK4083: recommended dose, i.e., one of three dose levels in Cohorts 1 - 3 based on the safety data from Part A, or placebo) once every 2 weeks (Weeks 0 to 10).
- b: Complete physical examinations include general appearance and examination of the HEENT and body systems (cardiovascular, respiratory, abdominal, musculoskeletal, extremities, lymph nodes, and skin).
- c: Brief physical examinations only include the HEENT, cardiovascular, respiratory, and abdominal examinations.
- d: Vital signs include systolic and diastolic blood pressure, radial pulse, respiration rate, and oral body temperature.
- e: Perform ECG pre-dose and at the end of infusion.
- f: If the subject does not continue in OLE Therapy, a sample for the multiplex-31 assay will also be collected at one of the follow-up visits.
- g: Female subjects considered to be women of childbearing potential must have a negative pregnancy test at Screening and Baseline. Subjects are considered to not be of childbearing potential if they are ≥ 50 years of age and without menses for 24 consecutive months; have an FSH level > 25 mIU/mL (or in postmenopausal range per local laboratory standards); or have undergone a hysterectomy and/or a bilateral salpingo-oophorectomy.
- h: Subjects with a low risk of an infection only need an interferon gamma release assay.
- i: For the delayed-type hypersensitivity test, the skin testing site will be read within 48 to 72 hours following intradermal injection of the *Candida albicans* antigen. The largest diameter of induration will be measured in mm and collected.
- j: If the subject discontinues more than 8 weeks after the Baseline visit, a sigmoidoscopy must be performed at End-of-Treatment. The sigmoidoscopy may be performed up to 4 weeks after the last dose of study medication.
- k: Fecal calprotectin concentration, which is usually elevated in subjects with moderately active UC, will be measured. Fecal samples will be collected as specified in the stool collection instruction section of the laboratory manual.
- l: Samples for anti-KHK4083 antibodies must be taken prior to dosing and taken at the same time as pre-dose PK samples shown in Table 10.4.1-1 and Table 10.4.1-2.
- m: Whole blood will be collected and stored (frozen) for potential exploratory biomarker analyses in the future at: Baseline (Week 0), Week 2, Week 12 (End-of-Induction Therapy), and Induction Therapy Post-treatment Follow-up 3 visit (if the subject does not continue in OLE Therapy).
- n: The collection of adverse event information should commence following the subject’s written consent to participate in the study.

Footnotes to Table 9-1.(cont'd)

o: All medications (including prescription, non-prescription and supplements) for treatment of UC taken within 6 months prior to Screening; any other medication taken 1 month prior to Screening; and any concomitant medications (including tracking probiotic usage) during the study must be recorded. For all biologic treatments, the reason for discontinuation should be recorded at Screening.

p: All subjects are required to remain at the investigative site to be carefully monitored after each infusion for potential infusion reactions or other adverse events. Post-infusion safety monitoring is as follows:

Week 0 (Day 1 Baseline): minimum of 3 hours post-infusion at site and a phone call at approximately 48 to 72 hours post-infusion for any subject who does not return for the scheduled visit at the investigative site;

Week 2: minimum of 3 hours post-infusion at site and a phone call at approximately 48 to 72 hours post-infusion for any subject who does not return for a visit at the investigative site;

Weeks 4, 6, 8 and 10: minimum of 1 hour post-infusion at site.

CBC=complete blood count; ECG=electrocardiogram; eCRF=electronic case report form; FSH=follicle-stimulating hormone; HEENT=head, eyes, ears, nose, and throat; HIV=human immunodeficiency virus; IBDQ=Inflammatory Bowel Disease Questionnaire; LTE=long-term extension; mMES=modified Mayo endoscopy subscore; OLE=open-label extension; PK=pharmacokinetic(s); PPD=purified protein derivative; TB=tuberculosis; UC=ulcerative colitis; UCEIS=Ulcerative Colitis Endoscopic Index of Severity; US=United States; wr-CRP=wide-range C-reactive protein.

Table 9-2 Study Schedule of Events - Open-label/Long-term Extension Maintenance Therapy and Follow-up Period

Procedure	Treatment Period - OLE/LTE Therapy: Week 12 (First Dose) to Week 52 ^a											OLE/LTE Therapy Post-treatment Follow-up Period			
	Week 12											End-of-OLE/LTE Therapy	Follow-up 1	Follow-up 2	Follow-up 3
		Week 16 ± 7 days	Week 20 ± 7 days	Week 24 ± 7 days	Week 28 ± 7 days	Week 32 ± 7 days	Week 36 ± 7 days	Week 40 ± 7 days	Week 44 ± 7 days	Week 48 ± 7 days	Week 52 ± 7 days	Week 56 ± 7 days	Week 60 ± 7 days	End-of-Study Week 64 ± 7 days	
Inclusion/Exclusion Criteria ^b	X														
Physical Examination ^c	X										X				
Brief Physical Examination ^d		X	X	X	X	X	X	X	X	X		X	X	X	
Vital Signs ^e	X	X	X	X	X	X	X	X	X	X	X	X	X	X	X
Body Weight	X	X	X	X	X	X	X	X	X	X	X	X	X	X	X
12-lead ECG	X ^f	X ^f									X				
Hematology (CBC with diff & platelets)	X	X	X	X	X	X	X	X	X	X	X	X	X	X	X
Serum Chemistry Profile	X	X	X	X	X	X	X	X	X	X	X	X	X	X	X
Coagulation Profile	X										X				
Multiplex-31 Assay	X										X				
Urinalysis	X	X	X	X	X	X	X	X	X	X	X	X	X	X	X
Serum Pregnancy ^g											X				
Urine Pregnancy ^g	X	X	X	X	X	X	X	X	X	X	X	X	X	X	X
Stool Enteric Pathogens (including Clostridium difficile)	X										X				
Partial Mayo Clinic Score (without sigmoidoscopy, includes review of diary) with Physician's Global Assessment	X	X	X	X	X	X	X	X	X	X	X	X	X	X	X

Table 9-2 Study Schedule of Events - Open-label/Long-term Extension Maintenance Therapy and Follow-up Period

Procedure	Treatment Period - OLE/LTE Therapy: Week 12 (First Dose) to Week 52 ^a											OLE/LTE Therapy Post-treatment Follow-up Period			
	Week 12											End-of-OLE/LTE Therapy	Follow-up 1	Follow-up 2	Follow-up 3
		Week 16 ± 7 days	Week 20 ± 7 days	Week 24 ± 7 days	Week 28 ± 7 days	Week 32 ± 7 days	Week 36 ± 7 days	Week 40 ± 7 days	Week 44 ± 7 days	Week 48 ± 7 days	Week 52 ± 7 days	Week 56 ± 7 days	Week 60 ± 7 days	End-of-Study Week 64 ± 7 days	
Flexible Sigmoidoscopy with biopsy for mMES, UCEIS, modified Baron score & total Mayo Clinic score (includes review of diary)	X (recommend 7 to 13 days prior to Week 12)										X ^h (at visit or within 21 days prior to Week 52)				
IBDQ	X	X	X	X	X	X	X	X	X	X	X	X	X	X	
Fecal Calprotectin ⁱ	X										X				
wr-CRP Assay	X			X			X				X			X	
Pharmacokinetics	For PK Sample Collection Schedule Refer to Table 10.4.1-1 for Cohorts 1 - 3 during Induction Therapy (Part A) and OLE/LTE and Table 10.4.1-2 for Cohort 4 during Induction Therapy (Part B) and OLE/LTE														
Anti-KHK4083 Antibodies ^j	X	X	X	X	X	X	X	X	X	X	X	X	X	X	
Flow Cytometry	Refer to Table 10.4.1-1 for Cohorts 1 - 3 and Table 10.4.1-2 for Cohort 4														
Future Biomarker Analyses (whole blood) ^k	X										X			X	
Adverse Events	X	X	X	X	X	X	X	X	X	X	X	X	X	X	
Concomitant Medications ^l	X	X	X	X	X	X	X	X	X	X	X	X	X	X	
Investigational Product Administration ^a On-site Post-infusion Monitoring Required^m	X	X	X	X	X	X	X	X	X	X					

Footnotes to Table 9-2

- a: The OLE Therapy Dosing Regimen: 10 KHK4083 treatments to be administered as one IV infusion every 4 weeks (Weeks 12 to 48) at the dose administered to the subjects in the cohort (or a lower dose if that cohort is discontinued) during Induction Therapy. LTE Therapy Dosing Regimen: 10 additional KHK4083 or placebo treatments to be administered as one IV infusion every 4 weeks (Weeks 12 to 48) at the dose administered to the subjects in the cohort (or a lower dose if that cohort is discontinued) during Induction Therapy. Subjects in LTE who transition to the OLE should have visits and assessments as described in Section 6.1.4.
- b: Subjects who complete double-blind Induction Therapy must meet additional eligibility criteria (refer to Section 7.4) to receive OLE Therapy once every 4 weeks (first dose at Week 12) with a post-treatment Follow-up Period for 16 weeks after the subject's last infusion. The treatment at Week 12 will be administered at the scheduled visit or within 7 days after Week 12. Subjects participating in the double-blind LTE who experience a clinical worsening or a flare of disease up to Week 28, as defined by the Investigator, may transition to the OLE (refer to Section 6.1.4).
- c: Complete physical examinations include general appearance and examination of the HEENT and body systems (cardiovascular, respiratory, abdominal, musculoskeletal, extremities, lymph nodes, and skin).
- d: Brief physical examinations only include the HEENT, cardiovascular, respiratory, and abdominal examinations.
- e: Vital signs include systolic and diastolic blood pressure, radial pulse, respiration rate, and oral body temperature.
- f: Perform ECG predose and at the end of infusion. Subjects who transition from LTE to OLE must have ECGs performed predose and at the end of infusion for the first two infusions.
- g: Female subjects considered to be women of childbearing potential must have a negative pregnancy test at Screening and Baseline. Subjects are considered to not be of childbearing potential if they are ≥ 50 years of age and without menses for 24 consecutive months; have a follicle-stimulating hormone level > 25 mIU/mL (or in postmenopausal range per local laboratory standards); or have undergone a hysterectomy and/or a bilateral salpingo-oophorectomy.
- h: If the subject discontinues more than 8 weeks after the Week 12 visit, a sigmoidoscopy must be performed at End-of-Treatment. The sigmoidoscopy may be performed up to 4 weeks after the last dose of study medication.
- i: Fecal calprotectin concentration, which is usually elevated in subjects with moderately active UC, will be measured.
- j: Samples for anti-KHK4083 antibodies must be taken prior to dosing and taken at the same time as pre-dose PK samples shown in the Table 10.4.1-1 and Table 10.4.1-2.
- k: Whole blood will be collected and stored (frozen) for potential exploratory biomarker analyses in the future at Week 52 (End-of-OLE/LTE Therapy) and at the OLE/LTE Therapy Post-treatment Follow-up 3 visit.
- l: Record concomitant medications during the study and probiotic usage.
- m: All subjects are required to remain at the investigative site to be carefully monitored after each infusion for potential infusion reactions or other adverse events. Post-infusion safety monitoring is as follows:
 - Week 12 (first dose in OLE Therapy) or first dose in subjects who transition from LTE to OLE: minimum of 3 hours post-infusion at site and a phone call at approximately 48 to 72 hours post-infusion for any subject who does not return for a visit at the investigative site;
 - Week 16 (second dose in OLE Therapy) or second dose in subjects who transition from LTE to OLE : minimum of 3 hours post-infusion at site and a phone call at approximately 48 to 72 hours post-infusion for any subject who does not return for a visit at the investigative site;
 - All other doses in OLE after the first 2 doses: minimum of 1 hour post-infusion at site.

CBC=complete blood count; ECG=electrocardiogram; HEENT=head, eyes, ears, nose, and throat; IBDQ=Inflammatory Bowel Disease Questionnaire; IV=intravenous; LTE=long-term extension; mMES=modified Mayo endoscopy subscore; OLE=open-label extension; PK=pharmacokinetic(s); UC=ulcerative colitis; UCEIS=Ulcerative Colitis Endoscopic Index of Severity; wr-CRP=wide-range C-reactive protein.

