
200 mg SC followed by at least 100 mg at least 2 weeks apart and anti-TNF biosimilar products with approved dosages for 2 doses at least 2 weeks apart; or as maintenance therapy for recurrence of symptoms despite continued dosing, or history of intolerance (including but not limited to infusion or injection reactions, demyelination or infection).
 
7) Female subjects who are considered to be women of childbearing potential (WOCBP) must have a negative pregnancy test at Screening and Baseline. WOCBP must agree to use effective contraception, defined as oral contraceptives with one barrier method, or tubal ligation with one barrier method or double barrier method (condom plus spermicide or diaphragm plus spermicide) during the study and for at least 6 months after the last dose of investigational product. Subjects are considered to not be of childbearing potential if they are ≥ 50 years of age and without menses for 24 consecutive months and have a follicle-stimulating hormone level > 25 mIU/mL (or in postmenopausal range per local laboratory standards); or have undergone a hysterectomy and/or a bilateral salpingo-oophorectomy. Egg donation is not permitted while on study medication and for at least 6 months after the last dose of study medication.
 
8) Male subjects (including those who have had a vasectomy) must use adequate contraception (e.g., latex condom, non-latex condom not made of natural animal membrane such as polyurethane condom) during the study and for at least 6 months after the last dose of investigational product. Sperm donation is not permitted while on study medication and for at least 6 months after the last dose of study medication.
 
Subjects must be excluded from participating in this study if they meet any of the following Exclusion Criteria:
 
 1) Subject, who, for any reason, is judged by the Investigator to be inappropriate for this study, including a subject who is unable to communicate or cooperate with the Investigator, who has/had a psychiatric illness, disability or social situation that may compromise the safety of the subject during the study or affect the ability of the subject to adhere to study procedures; 2) Subject has a medical history of clinically significant (as determined by the Investigator or the Sponsor) cardiac, renal, hepatic/biliary (e.g., sclerosing cholangitis), pulmonary, or other medical conditions or is not generally in good health. Subjects with the history of immunologic, autoimmune or chronic inflammatory disorders (e.g., uveitis, rheumatoid arthritis, ankylosing spondylitis or spondyloarthritis, psoriasis) other than UC or autoimmune connective tissue diseases (e.g., systemic lupus erythematosus, systemic sclerosis) and are well controlled may be included into the trial after consultancy with medical monitor. Subjects with thyroid disorders, vitiligo, or alopecia are eligible for inclusion. 3) Subject's UC had failed to respond to: 
 a) Two or more biologic treatments with different mechanisms of action (e.g., infliximab and vedolizumab), or b) Three or more anti-TNF biologics (e.g. infliximab, adalimumab, and golimumab). 4) Subject requires prescription treatment for UC, except for the stable, oral treatment of UC, as follows: 
 a) Aminosalicylates (5-aminosalicylic acid [5-ASA] or mesalamine ≤ 4.8 g/day; sulfasalazine 		

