 - c) tumor necrosis factor-alpha antagonists for induction therapy with approved anti-TNF products including, but not limited to, infliximab 5 mg/kg IV for 2 doses at least 2 weeks apart, adalimumab 160 mg SC followed by at least 80 mg SC at least 2 weeks apart, and golimumab 200 mg SC followed by at least 100 mg at least 2 weeks apart and anti-TNF biosimilar products with approved dosages for 2 doses at least 2 weeks apart; or as maintenance therapy for recurrence of symptoms despite continued dosing, or history of intolerance

(including but not limited to infusion or injection reactions, demyelination or infection).

- 7) Female subjects who are considered to be women of childbearing potential (WOCBP) must have a negative pregnancy test at Screening and Baseline. WOCBP must agree to use effective contraception, defined as oral contraceptives with one barrier method, or tubal ligation with one barrier method or double barrier method (condom plus spermicide or diaphragm plus spermicide) during the study and for at least 6 months after the last dose of investigational product. Subjects are considered to not be of childbearing potential if they are ≥ 50 years of age and without menses for 24 consecutive months and have a follicle-stimulating hormone (FSH) level > 25 mIU/mL (or in postmenopausal range per local laboratory standards); or have undergone a hysterectomy and/or a bilateral salpingo-oophorectomy.
Egg donation is not permitted while on study medication and for at least 6 months after the last dose of study medication.
- 8) Male subjects (including those who have had a vasectomy) must use adequate contraception (e.g., latex condom, non-latex condom not made of natural animal membrane such as polyurethane condom) during the study and for at least 6 months after the last dose of investigational product.
Sperm donation is not permitted while on study medication and for at least 6 months after the last dose of study medication.

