10.6.1 Clinical Laboratory Evaluation

Clinical laboratory parameters assessed in this study are displayed in Table 10.6.1-1. The collection times for blood, urine, and fecal specimens during the study are specified in Table 9-1 and Table 9-2.

Table 10.6.1-1 Clinical Laboratory Assessments

Serum Chemistry^a	SGOT (AST) SGPT (ALT) Creatine kinase LDH Alkaline phosphatase Total bilirubin Folate Glucose	Creatinine Albumin BUN Sodium Potassium Calcium Vitamin B12	Chloride Total cholesterol Triglycerides Uric Acid Amylase Lipase
wr-CRP Assay	To be performed on serum chemistry samples at Week 0 (Baseline), all visits during Induction Therapy, Week 26 (only for subjects not continuing to OLE/LTE Therapy), and at Weeks 24, 36, 52, and 64.		
Multiplex-31 Assay	To be performed at Baseline (Week 0), Week 2, Week 12, and Week 52 or at a follow-up visit if the subject does not continue in OLE/LTE Therapy.		
Diabetes Screening	Subjects with glycated serum hemoglobin A1c \geq 9% will be excluded from the study.		
Coagulation Profile	prothrombin time partial thromboplastin time		
Hematology^a	Hemoglobin Hematocrit RBCs	WBC count Differential and absolute counts Platelet count	
Urinalysis	Color Specific Gravity pH Protein Glucose Ketones	Bilirubin Urobilinogen Occult blood Nitrites Microscopic examination, if clinically indicated, including RBCs, WBCs, casts, bacteria and crystals	
Urine Drug Screening	Barbiturates, Benzodiazepines, Amphetamines, Cocaine, Cannabinoids, Opiates, Methamphetamine, Alcohol, and Cotinine		
Serum FSH Test	To be performed on all presumed post-menopausal females at Screening. Post-menopausal females are defined as females with the complete absence of menses for 24 consecutive months; have an FSH level $>$ 25 mIU/mL (or in postmenopausal range per local laboratory standards) in the absence of hormone replacement therapy.		
Serum and/or Urine Pregnancy Test (minimum sensitivity 25 IU/L or equivalent units of β -HCG)	To be performed for all female subjects considered to be women of childbearing potential at Screening and at specified timepoints during the Treatment Period. Note: Subjects are considered to not be of childbearing potential if they are \geq 50 years of age and without menses for 24 consecutive months and have an FSH level $>$ 25 mIU/mL (or in postmenopausal range per local laboratory standards); or have undergone a hysterectomy and/or a bilateral salpingo-oophorectomy.		

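### Footnote g of Tables 9-1 and 9-2, read literally, exempts from pregnancy testing women whom Inclusion Criterion 7 classes as of childbearing potential

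*Protocol*

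**What the plan says.** The protocol defines the same status in several places.

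- **Inclusion Criterion 7, Section 7.2.** After an age limit of 50, the text continues "without menses for 24 consecutive months and have a follicle-stimulating hormone (FSH) level > 25 mIU/mL", with the laboratory's own postmenopausal range as an alternative to the FSH cut-off. Surgery (hysterectomy and/or removal of both tubes and ovaries) is a separate route. The Synopsis has the same construction: "without menses for 24 consecutive months and have a follicle-stimulating hormone level > 25 mIU/mL".
- **Pregnancy-test row of Table 10.6.1-1, Section 10.6.1.** This repeats the Inclusion 7 rule, with *and* before the FSH condition.
- **Table 9-1, footnote g.** "≥ 50 years of age and without menses for 24 consecutive months; have an FSH level > 25 mIU/mL", followed by the local-range alternative, another semicolon, and *or* before surgery. The footnote is attached to the Serum FSH, Serum Pregnancy and Urine Pregnancy rows. It opens by saying whom it governs: "Female subjects considered to be women of childbearing potential must have a negative pregnancy test at Screening and Baseline".
- **Table 9-2, footnote g.** The same punctuation: "without menses for 24 consecutive months; have a follicle-stimulating hormone level > 25 mIU/mL". It is attached to both pregnancy-test rows of the extension schedule.
- **Serum FSH row of Table 10.6.1-1.** "Post-menopausal females are defined as females with the complete absence of menses for 24 consecutive months; have an FSH level $>$ 25 mIU/mL", qualified by the absence of hormone replacement therapy. It gives no age limit.

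**The concern.** Inclusion 7 joins three conditions with *and*. Footnote g replaces the second *and* with a semicolon, in a list closed by *or*. On its face that makes raised FSH sufficient alone, and also makes age with amenorrhea sufficient without any FSH condition.

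The footnote is attached to the rows from which sites schedule the tests, and it restates the exemption in full without pointing to Inclusion 7. A site working from the schedule therefore has a complete rule that differs from the eligibility rule and is less protective. Inclusion 7 itself names only the Screening and Baseline tests; the later visits at which tests fall due are set in the schedule tables. Pregnancy is an exclusion (Section 7.3, criterion 12) and, once confirmed on treatment, leads to permanent discontinuation and withdrawal (Section 7.5.3). The classification is thus part of how the protocol guards against fetal exposure.

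**Working it through.** There is no sample size, power or error rate to reproduce. The check compares the definitions clause by clause.

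**Inputs.** For a woman without qualifying surgery, let A = age 50 or over, M = no menses for 24 months, F = FSH above 25 mIU/mL or in the local postmenopausal range.

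- Inclusion 7, Synopsis and pregnancy-test row: exempt if A and M and F.
- Footnote g, both tables, as punctuated: exempt if (A and M) or F.

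**All eight combinations.**

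| A | M | F | Inclusion 7 | Footnote g |
|---|---|---|---|---|
| no | no | no | test | test |
| no | no | yes | test | **exempt** |
| no | yes | no | test | test |
| no | yes | yes | test | **exempt** |
| yes | no | no | test | test |
| yes | no | yes | test | **exempt** |
| yes | yes | no | test | **exempt** |
| yes | yes | yes | exempt | exempt |

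Inclusion 7 exempts 1 of 8 and footnote g exempts 5 of 8. The difference, 5 − 1 = 4, consists wholly of women of childbearing potential under Inclusion 7:

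- F met, but under 50 or still menstruating within the 24 months (three rows);
- 50 or over with 24 months' amenorrhea, but F not met (one row).

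**Two illustrations.** A 44-year-old with 24 months' amenorrhea and FSH 30 must be tested under Inclusion 7 and is exempt under the footnote. So is a 52-year-old with 24 months' amenorrhea and FSH 15, assuming 15 lies outside her laboratory's postmenopausal range.

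**Tests at stake for one woman**, counting Week 12 once although it appears in both tables:

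- Induction and its follow-up only: serum at Screening (1); urine at Weeks 0, 4, 8, 12, 16, 20 and 26 (7). Total 1 + 7 = 8.
- Induction, full extension and follow-up: serum at Screening and Week 52 (2); urine at Weeks 0, 4, 8 and 12 (4), every four weeks from Week 16 to Week 52 (10), and at Weeks 56, 60 and 64 (3). Total 2 + 4 + 10 + 3 = 19.

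**Serum FSH row (secondary).** If its semicolon means *and*, its definition of post-menopausal covers 2 of the 8 combinations, one more than Inclusion 7 (under 50 with amenorrhea and FSH). If it means *or*, it covers 6. The row says who receives an FSH test; it does not say who is excused a pregnancy test.

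**The case against.** The best defence is that this is a drafting slip in one footnote, used twice, and that Inclusion 7 governs. Three places agree on the three-part rule and only the footnotes depart from it. Section 9.1 requires every subject to satisfy the criteria in Sections 7.2 and 7.3 and lists childbearing potential as a Screening assessment. Sections 9 and 9.2 require review of eligibility before randomization. FSH is scheduled only at Screening, and Table 9-2 has no FSH row, so nothing in the schedule calls for later reclassification. Table 10.6.1-1 directs FSH testing to presumed post-menopausal women, so a menstruating woman would seldom have an FSH value with which to use the footnote's FSH-only route.

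Most of this stands, and it lowers the chance of harm. It does not remove the contradiction. No passage says which definition prevails for scheduling tests, and the footnote is the text attached to those rows. The sponsor has treated a similar mismatch as worth correcting: Amendment 2 changed Exclusion Criterion 4 to bring it into line with Inclusion Criterion 6.

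Three stronger readings are tempting, and the documents do not support them.

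- *The Serum FSH row also exempts women from testing.* It does not. It defines post-menopausal for the FSH test, and the next row, on pregnancy tests, carries the Inclusion 7 rule. Its missing age limit and its hormone-replacement condition, found nowhere else, are a secondary inconsistency.
- *Misclassified women would also go without contraception.* Footnote g says nothing about contraception. That duty is set in Inclusion 7, beside the three-part definition, so a site applying it is reading the stricter text.
- *The deviation would go unnoticed.* Medical Monitoring meetings review adherence to the inclusion and exclusion criteria (Section 6.3). SAP Section 9.6 lists protocol deviations, eligibility violations and pregnancy tests for randomized subjects. A missed test may well be found, though possibly only after dosing.

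**Conclusion.** The concern holds as an internal inconsistency, wrong as written. It is not a design choice that the sponsor argued for. Footnote g of Tables 9-1 and 9-2, taken literally, exempts from scheduled pregnancy tests two groups of women without surgery whom Inclusion 7 classes as of childbearing potential:

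- those meeting the FSH criterion who are under 50 or still have menses;
- those aged 50 or over with 24 months' amenorrhea whose FSH is neither above 25 mIU/mL nor in the local postmenopausal range.

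In terms of combinations the gap is 5 exempt against 1. For an individual woman it is 8 tests if she leaves after induction and its follow-up, and 19 if she completes the extension and its follow-up. The documents give no basis for estimating how many women fall in the gap.

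The conclusion rests on reading the semicolons and the closing *or* at face value. A reader who took the footnote as shorthand for Inclusion 7 would see no difference in practice. Efficacy, sample size, power and the analysis are unaffected. The point should be corrected because it concerns a safety classification and correction is nearly free. Which definition is clinically right is not judged here.

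**What to change.** The passages must be reconciled. State one definition in Inclusion Criterion 7, in Section 7.2 and the Synopsis alike. Replace the wording in footnote g of Table 9-1, footnote g of Table 9-2, and the Serum FSH and pregnancy-test rows of Table 10.6.1-1 with a cross-reference to it. The sponsor's clinicians should choose the definition, and should decide whether the hormone-replacement condition belongs in it.

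The cost is an edit to the protocol text. If the three-part rule is kept, any extra testing is limited to tests already in the schedule. No analysis or table in the SAP needs to change.
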